### 9.2. Determining Reference Invasive Blood Pressure Per ISO 81060-2:2013

First, the mean and the standard deviation of the invasive blood pressures derived from the IBP wave recordings during a NIBP determination will be calculated; and the range of reference invasive blood pressure will be determined as mean  $\pm 1$  standard deviation (SD) of the IBPs. The same method will be used for both systolic and diastolic blood pressures. Calculation of reference IBP from IBP wave recordings is not part of the statistical analysis. Data may be excluded for analysis when the range of invasive systolic BP is wider than 20 mmHg or when the range of invasive diastolic BP is wider than 12 mmHg, as such that analysis is performed in accordance with ISO 81060-2:2013.

#### 9.2.1. Analysis of Blood Pressure Measurement Error

The BP measurement error of the investigational device will be determined as follows:

- If the value obtained from the investigational device lies within the range of reference IBP, an error of 0 mmHg will be assigned to this determination.
- If the value obtained from the investigational device lies outside the range of the IBP, the error for this determination will be calculated by subtracting the

adjacent limit of the IBP range from the value of the NIBP determination ( $\Delta = \text{NIBP} - \text{IBP}$ ).

Then, mean and SD will be calculated from the errors of each determination of each patient using the following formulae, and will be compared to the acceptance criteria, i.e., mean  $\leq 5$  mmHg and SD  $\leq 8$  mmHg. Percentages of measurements with errors within 5 mmHg, 10 mmHg, and 15 mmHg will also be calculated.

Mean: 
$$\bar{x}_n = \frac{1}{n} \times \sum_{i=1}^n x_i$$

SD: 
$$s_n = \sqrt{\frac{1}{n-1} \times \sum_{i=1}^n (x_i - \bar{x}_n)^2}$$

In addition, Bland-Altman plot will be presented for the measurement agreement between NIBP and reference IBP. The ‘average’ (x-axis) represents the average of the blood pressure from the investigational device and the mean reference IBP value. The ‘difference’ (y-axis) is the blood pressure measurement difference calculated as  $\Delta = \text{NIBP} - \text{mean IBP}$ .

Population mean bias, between-subject variance, within-subject variance, and limits of agreement will be calculated for the measurement difference using Bland-Altman method as described in the article “Agreement Between Methods Of Measurement With Multiple Observations Per Individual” by Bland and Altman in 2007 Journal of Biopharmaceutical Statistics.

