## **2.2. Pre-Clinical (animal) Trials and Previous Clinical (human) Experience**

Previous study has indicated that the GE DINAMAP® SuperSTAT algorithm on the GE CARESCAPE Patient Monitor Series or DASH® Monitor Series is accurate in adult, children, and neonate patients, including hypotensive and hypertensive patients. Furthermore, the GE DINAMAP® SuperSTAT algorithm and the Datex Ohmeda GE algorithm have also been reported to satisfy the ANSI/AAMI SP10-2002 and SP10A-1996 American National Standard for Electronic or Automated Sphygmomanometers in adults and, for GE DINAMAP® SuperSTAT only, neonatal populations, meaning that all values were  $\pm 5$  mmHg with a standard deviation of  $\leq 8$  mmHg of reference standards.

The Datex-Ohmeda GE algorithm has been successfully used to monitor blood pressure in adult patients and to predict vascular change and fluid loading, demonstrating results similar to

reference standard intra-arterial monitors in 26 patients according to the Association for Advancement of Medical Instrumentation (AAMI) standards. Compared to other oscillometric blood pressure measurement algorithms, Datex Ohmeda GE was shown to be somewhat slower but equally accurate in a study involving 160 blood pressure recordings.

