## 4.2. Study Objectives

### 4.2.1. Primary Objective:

The primary objective of the study is to determine if the PSM-Datex-Ohmeda and PDM-SuperSTAT NIBP measurement devices provide accurate blood pressure measurements in all indicated patient populations (neonates, children, pediatrics, adolescents and adults, and special populations) according to the definitions set forth by ISO 81060-2:2013.

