## 4.3. Study Endpoints

### 4.3.1. Primary endpoints:

Per patient, NIBP and IBP endpoints will be collected for:

- Systolic BP (mmHg)
- Diastolic BP (mmHg)
- NIBP and IBP Mean Arterial Blood Pressure (MAP)

Per patient, for NIBP only:

- Accuracy, determined according to ISO 81060-2:2013

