## 9.6. Pass/Fail Criteria of the Study

The study will be considered to pass if a sufficient data set is collected to satisfy the requirements of ISO 81060-2:2013.

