## **17. ADDITIONAL STUDY MATERIALS / ADDITIONAL COUNTRY-SPECIFIC REGULATORY REQUIREMENTS**

The study will be conducted in accordance with all requirements of ISO 81060-2:2013. This study will be conducted in compliance with Good Clinical Practice, per international standards.

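### Section 9.2.1 puts no lower bound on the mean of a signed error, and Section 9.6 neither states an accuracy limit nor refers to 9.2.1

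*Combined protocol and SAP*

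**What the plan says.** **Error (9.2.1).** A device reading inside the reference range (mean invasive pressure ±1 SD, Section 9.2) gets an error of 0. Outside it, the error is found by subtracting the "adjacent limit of the IBP range from the value of the NIBP determination". The error therefore carries a sign: negative when the device reads low, positive when it reads high.

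**Limits (9.2.1).** The mean and SD of these errors "will be compared to the acceptance criteria, i.e., mean" ≤ 5 mmHg and SD ≤ 8 mmHg. The printed formula averages the signed values. The same section also asks for percentages within 5, 10 and 15 mmHg and for a Bland-Altman analysis, with no threshold on either.

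**Pass/fail (9.6).** "The study will be considered to pass if a sufficient data set is collected to satisfy the requirements of ISO 81060-2:2013". The section contains nothing else.

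**Links to the standard.** The accuracy endpoint in 4.3.1 is "Accuracy, determined according to ISO 81060-2:2013", and Section 17 says "The study will be conducted in accordance with all requirements of ISO 81060-2:2013". The primary objective (4.2.1) is to determine whether the devices "provide accurate blood pressure measurements in all indicated patient populations".

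**Pointer (4.1).** No hypothesis is set, because the aim is conformity with the standard. The reader is sent to Section 9.5 for the pass/fail criteria, but 9.5 covers missing data and the criteria are in 9.6.

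**The concern.** An upper limit alone on a signed mean controls bias in one direction only. A device that reads low by a steady amount satisfies it however large the shift, and one that reads high by the same amount does not. The SD limit cannot make up for this, because a constant shift does not alter an SD.

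The two limits in 9.2.1 are the only numeric accuracy criteria that the plan writes out for this study, and 9.6 does not say that they decide anything. An analyst programming from 9.2.1 would code a one-sided rule. A reader of 9.6 would not learn which section holds the limits, or that they must hold for each pressure and in each population. Sections 4.2.1, 9.1.1 and 9.2 point that way without saying it.

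**Working it through.** There is no sample size, alpha or power to reproduce: the limits are stated, not derived. The check applies the written rule to two mirror-image results.

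**Inputs, all from 9.2.1**
- Error x = NIBP − adjacent limit, or 0 inside the range.
- Mean = Σx / n. SD = √[Σ(x − mean)² / (n − 1)].
- Written rule: mean ≤ 5 and SD ≤ 8 (mmHg).
- Rule for comparison: −5 ≤ mean ≤ 5 and SD ≤ 8.

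**Step 1, the inequalities**

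| Mean error | SD | Written rule | Two-sided rule |
|---|---|---|---|
| −15 | 6 | −15 ≤ 5 and 6 ≤ 8: met | −15 < −5: not met |
| +15 | 6 | +15 > 5: not met | not met |

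**Step 2, the printed formulae on a constructed data set.** Take 150 errors (150 is the pair target per age group in Section 6.3), 75 of −26 mmHg and 75 of −14 mmHg.
- Mean = (75 × −26 + 75 × −14) / 150 = −3000 / 150 = −20.0.
- Every deviation from the mean is ±6, so SD = √(150 × 36 / 149) = √36.24 = 6.02.
- Written rule: −20.0 ≤ 5 and 6.02 ≤ 8, so both limits are met.
- Reversing every sign gives mean +20.0 and SD 6.02, and the mean limit fails.

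**Step 3, why the SD limit does not help.** Adding a constant c to every error moves the mean by c and leaves each deviation, and so the SD, unchanged. Any set of errors that meets SD ≤ 8 still meets it after a downward shift of any size.

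**Step 4, the other outputs.** In the constructed set no error lies within 5 or 10 mmHg, and 75 of 150 (50%) lie within 15 mmHg. These percentages would make the under-read obvious to anyone who looked, but the plan ties no pass condition to them.

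The constructed values test the rule. They say nothing about how either device performs.

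**The case against.** The strongest reply is that the operative rule is ISO 81060-2:2013. It governs the objective, the accuracy endpoint, the separate analyses in 9.1.1, the pass/fail sentence and the conduct of the study. The wording of 9.2.1 can be read as a short restatement of criteria held in the standard, and nothing in the plan says that the restatement overrides it. Section 2.2 describes results under earlier standards as "meaning that all values were" ±5 mmHg with SD ≤ 8 mmHg, which suggests that two-sided limits were in mind. A ± sign lost in document conversion also cannot be fully excluded, although the sign survives in 2.2 and 9.2.

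Most of this stands as a limit on the consequence. It does not remove the defect. If the standard's limit is two-sided, 9.2.1 misstates it and needs correcting. If a sign was lost, 9.6 still has no link to 9.2.1. The decision rule should not depend on inference from a background section.

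Three stronger readings are tempting, and the documents do not support them.
- *A low-reading device would be accepted.* That follows only if the wording of 9.2.1 were applied over the standard, whose text is not available here.
- *5 mmHg is the only numeric limit, so any low-reading device meets the written criteria.* The same sentence sets SD ≤ 8 mmHg, and that limit can still fail a low-reading device with widely scattered errors.
- *Section 9.6 passes the study on data collection alone.* Its sentence requires data that satisfy the standard, which may include accuracy limits.

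**Conclusion.** The point holds as a correction to the written decision rule. Section 9.2.1 sets two numeric limits on a signed error. The one on the mean is open below, so under-reads and over-reads of equal size are treated differently: −15 mmHg with SD 6 meets the rule and +15 mmHg with SD 6 does not. Section 9.6 supplies no accuracy limit and no reference to 9.2.1.

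This rests on a literal reading of the text and on arithmetic, with no assumption about device performance. A two-sided limit was probably meant, and the standard may impose one. Whether it does cannot be checked from these documents, so the finding gives no estimate of the risk of wrong acceptance. The wrong pointer in 4.1 is clerical.

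**What to change.** - **9.2.1:** state the limits as −5 ≤ mean error ≤ +5 mmHg and SD ≤ 8 mmHg, after checking them against the text of ISO 81060-2:2013.
- **9.6:** keep the existing sentence on the standard. Add that a device passes in a Section 9.1.1 analysis population only if the 9.2.1 limits are met for systolic and for diastolic pressure separately, together with any further criterion in the standard.
- **9.6, exclusions:** the last sentence of 9.1.1 lets the sponsor leave out a sub-population in which accuracy is compromised, which could bypass the new rule. Add that such a sub-population is reported and is not counted as passing.
- **4.1:** change the pointer from 9.5 to 9.6.

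The cost is one inequality, two added sentences and one cross-reference. No extra patients, data or analyses are needed. The role of mean arterial pressure and the patient and pair counts are separate matters and should be handled separately.

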### 9.2.2. Effect of Arm Circumference on Blood Pressure Measurement Error

A scatter plot of the percent difference in blood pressure measurement over arm size will be presented to evaluate the effect of arm size on measurement error. The percent difference will be calculated as:

$$\text{Percent Different} = \frac{\text{Difference between NIBP and Mean Reference IBP}}{\text{Average of NIBP and Mean Reference IBP}}$$

This analysis will be done for systolic and diastolic blood pressure separately by study arm.

### 9.2.3. Summary of Blood Pressure Measurement

Number of NIBPs taken from each subject, and total number of NIBPs will be summarized for each analysis population by study arm.

### 9.3. Analysis of Subject Characteristics

The following subject characteristics data will be summarized using descriptive statistics if applicable per standard requirements for each analysis population by study arm. Continuous

variables will be described using mean, standard deviation, median, minimum and maximum. Categorical variables will be described using count and percentage.

- Number of Adult/adolescents/children/atrial fibrillation patients
- Number of patients <1000g, 1000-2000g,>2000g in weight
- Number of patients <29 days, ≥29 days and < 1 year of age, ≥ 1 year and < 3 years of age, ≥ 3 year and ≤ 12 years of age
- Number of patients over 5 kg (11 lbs) and meet one of the following: ≥29 days and < 1 year of age, ≥ 2 year and < 3 years of age
- Gender
- Height and weight
- Arm Size
- Age
- Adult and adolescent subjects with mean invasive systolic blood pressure ≥ 160 mmHg
- Adult and adolescent subjects with mean invasive systolic blood pressure ≤ 100 mmHg
- Adult and adolescent subjects with mean invasive diastolic blood pressure ≥ 85 mmHg
- Adult and adolescent subjects with mean invasive diastolic blood pressure ≤ 70 mmHg
- Number of subjects tested on each cuff size
- Arterial sites where IBP was taken
- Heart rate

### 9.3.1. Data Exclusion

The following NIBP data will be excluded from analysis:

- NIBP data from a subject if the range of reference systolic blood pressure is more than 20mmHg or the range of reference diastolic blood pressure is more than 12 mm Hg, or as specified per ISO 81060-2:2013 standard;
- Measurements beyond 10 valid measurements for each subject;
- Isolated premature ventricular contractions (PVC) will be addressed by removing the pressure associated with the PVC and the following compensatory beat. The PVC will be identified through analysis of the ECG waveform associated with the PVC and pulses. This is done during calculating IBPs from the IBP wave form, not in the statistical analysis.

## 9.4. Interim Analysis

No interim analysis is planned. As necessary for study conduct, engineering, and/or regulatory purposes, study data may be accessed and, if necessary, reported by the Sponsor prior to closure of the study.

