### 6.3. Number of Subjects

The total minimum enrollment for the two study arms is 83 total evaluable patients (maximum of 200 patients), as follows:

1. **PDM-SuperSTAT Arm ( $N_{PDM}$ ):** 45 evaluable patients with GE DINAMAP® SuperSTAT algorithm (PDM Module) on CARESCAPE Monitor B650, to achieve a total target of  $\geq 150$  BP data pairs in patients  $\geq 3$  years old (up to 10 paired measurements per subject) and  $\geq 150$  BP data pairs in patients  $< 3$  years old (as described in Table 2).
2. **PSM-Datex-Ohmeda Arm ( $N_{PSM}$ ):** 29 evaluable patients with Datex-Ohmeda algorithm (PSM module) on CARESCAPE Monitor B650, to achieve a total of  $\geq 150$  BP data pairs in patients  $\geq 3$  years old (up to 10 paired measurements per subject) and  $\geq 150$  BP data pairs in patients  $< 3$  years old (as described in Table 2).

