### 6.3.1. Stratification of Subjects

Subject enrollment will be stratified based on prospective criteria to ensure diversity in the population, as described in ISO 81060-2:2013 and set forth in Table 1. Patients will be enrolled concurrently in both arms until all minimum quotas are reached, and thereafter up to the maximum enrollment for the study. Incomplete/non-evaluable datasets, as determined by the Sponsor, will not be considered to satisfy minimum requirements in Table 1. Additionally, multiple cuff sizes will be used, including a minimum of  $1/(2 \times n)$  per stratification group (except for the children/infants/neonates group), where  $n$  is the total within a stratification group able to be tested using the cuff in accordance with its labeling (Table 1).

**Table 1** – Summary of Patient Enrollment Stratification by Characteristics

Enrollment Stratification	Minimum Total in PDM-SuperSTAT arm	Minimum Total in PSM-Datex-Ohmeda arm	Age (years) requirement	Weight (g) requirement	Gender (M/F)	Minimum number of patients (n)	
Adults and Adolescents (General population) b	15 total patients	15 total patients	>12 yr	(no weight requirement)	F #	$n \geq 5$	
			>12 yr		M #	$n \geq 5$	
Adults and Adolescents Chronic Atrial Fibrillation b	7 total patients	-	>12 yr		M or F #	$n \geq 7$	
Pediatrics	5 total patients	5 total patients	$\geq 3$ AND $< 12$ yr		F #	$n \geq 2$	
			$\geq 3$ AND $< 12$ yr		M #	$n \geq 2$	
Children/Infants/ Neonates	18 total patients	-	$\geq 1$ yr AND $< 3$ yr		M or F	$n \geq 3$	
			>29 days AND $< 1$ yr		M or F	$n \geq 3$	
			(no age requirement)*		< 1000 g	M or F	$n \geq 3$
					1000-2000 g	M or F	$n \geq 3$
	-	9 total patients	>2000 g		M or F	$n \geq 3$	
			$\geq 1$ yr AND $< 3$ yr	>5 kg (~11 lbs) a	M or F	$n \geq 3$	
			>29 days AND $< 1$ yr	>5 kg (~11 lbs) a	M or F	$n \geq 3$	
			(no age requirement)*	>5 kg (~11 lbs) a	M or F	$n \geq 3$	
TOTAL	45 TOTAL	29 TOTAL					

**Abbreviations:** M = male; F = female;  $n$ , number of patients

\* No age requirement within the children/infant/neonates category may include subjects aged birth to  $< 3$  yrs

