### 7.4. Withdrawal and Discontinuation Criteria

The patient may withdraw from study participation at any time, for any reason without consequence. The Investigator may withdraw a patient at any time for any reason. The reasons for withdrawal and discontinuation for any patient shall be recorded. These will be reported to the Sponsor. The EC/IRB should be notified per their notification of patient withdrawal policy.

Data collected up until the time of withdrawal may still be disclosed to the Sponsor as part of this study to ensure the integrity of research data.

Continuation and discontinuation of enrollment in any stratification group will be made at the discretion of the Sponsor in the context of applicable regulatory and standards requirements, and the Investigator will be notified by the Sponsor upon such a determination.

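### The plan permits, without planning it, enrolment decisions informed by observed accuracy, and its two statements of when enrolment ends conflict

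*Combined protocol and SAP*

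**What the plan says.** **Access to data.** Section 9.4 states "No interim analysis is planned". It then says that, for study conduct, engineering or regulatory purposes, "study data may be accessed and, if necessary, reported by the Sponsor prior to closure of the study". It sets no limit on which data may be seen or how often. Section 5.1 describes the study as open-label. The amendment log (Appendix D, item 81) explains the access sentence, which is still in force, as clarifying that unplanned interim analyses may be done.

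**Authority to stop.** Section 7.4 says that continuation and discontinuation of enrolment in "any stratification group will be made at the discretion of the Sponsor in the context of applicable regulatory and standards requirements". Those requirements are not listed there.

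**When enrolment ends.** Section 6.3: "The total minimum enrollment for the two study arms is 83 total evaluable patients (maximum of 200 patients), as follows". The arm minimums that follow are "45 evaluable patients with GE DINAMAP® SuperSTAT algorithm (PDM Module) on CARESCAPE Monitor B650" and "29 evaluable patients with Datex-Ohmeda algorithm (PSM module) on CARESCAPE Monitor B650", with a target of at least 150 data pairs per arm in each of two age groups (3 years and over, under 3 years). Section 6.3.1: "Patients will be enrolled concurrently in both arms until all minimum quotas are reached, and thereafter up to the maximum enrollment for the study". Section 5.2 instead lets consecutive enrolment, once the quotas are met, run until the minimum total is reached.

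**Pass rule.** Section 9.2.1 compares the mean and SD of the errors over all determinations with 5 and 8 mmHg, with no confidence bound. Section 4.1 states that no statistical hypothesis is required.

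**The concern.** Four features act together: the final number is not settled, the sponsor may see unblinded data early, the sponsor decides when each group stops, and the criterion is a point estimate with no allowance for sampling error. A running SD moves up and down as patients are added. Someone who may watch it and choose when to stop has several chances to find it at or under 8 mmHg, where a single analysis has one.

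The possible consequence is a device whose true error SD lies a little above the limit being reported as meeting it. More patients should make that less likely. Under repeated looks with freedom to stop, they make it more likely.

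**Working it through.** **1. The plan's own floor.** Section 6.3 gives a combined minimum of 83. The arm minimums sum to 45 + 29 = 74. Table 1 agrees with the arms: 15 + 7 + 5 + 18 = 45 and 15 + 5 + 9 = 29. So 83 is not reproduced. Room up to the cap is 200 − 74 = 126 patients, or 200 − 83 = 117.

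**2. Earliest possible stop in each analysis population (Section 9.1.1).** At most 10 determinations per patient are analysed (Section 9.3.1), so 150 pairs need at least 150/10 = 15 patients.
- PDM, 3 years and over: quota 15 + 7 + 5 = 27 (up to 270 pairs)
- PDM, under 3 years: quota 18 (up to 180 pairs)
- PSM, 3 years and over: quota 15 + 5 = 20 (up to 200 pairs)
- PSM, under 3 years: quota 9 gives at most 90 pairs, so at least 15 patients are needed

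**3. Model.** The documents give no error SD, correlation, alpha or power, so the following are assumptions. Error j in patient i is x_ij = a_i + e_ij, with a_i ~ N(0, ρσ²) and e_ij ~ N(0, (1 − ρ)σ²). There are 10 pairs per patient, zero bias, and one pressure. With n patients the device passes if |x̄| ≤ 5 and s ≤ 8, using the mean and the n − 1 SD of Section 9.2.1 over all 10n errors. Taking the absolute value of the mean is my reading. The spare 126 patients are shared over the four populations: 126/4 = 31.5, taken as 31, so the first population runs from 27 to 27 + 31 = 58. Each setting was simulated at least 10,000 times.

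**4. Chance of passing, PDM aged 3 years and over, ρ = 0.5**

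| True SD (mmHg) | One analysis at 27 | Look after every patient, 27 to 58 |
|---|---|---|
| 8.0 (at the limit) | 58% | 78% |
| 8.5 | about 28% | 40% to 42% |
| 9.0 | 9% | about 13% |
| 10.0 | under 1% | under 1% |

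At true SD 8.5, a look every 10 patients gives about 37%, and a single analysis at 58 gives about 15%.

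**5. Sensitivity at true SD 8.5**
- Correlation 0.3 to 0.7: 18% to 35% at a fixed 27; 29% to 51% with a look after every patient; 8% to 23% at a fixed 58.
- All 126 spare patients in this one population (27 to 153), ρ = 0.5: 28% at a fixed 27, 45% with looks, 4% at a fixed 153.
- Other populations, ρ = 0.5, fixed minimum against looks after every patient: PDM under 3 years (18 to 49) 34% and 52%; PSM 3 years and over (20 to 51) 33% and 49%; PSM under 3 years (15 to 46) 36% and 54%.
- Systolic and diastolic both required to pass, with an assumed correlation of 0.5 between them (27 to 58): 10% rises to 19%.

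**The case against.** **Nothing ties enrolment to the observed SD.** No interim analysis is planned, and early access is confined to three stated purposes. A reader might infer that enrolment is designed to end once the SD drops under 8 mmHg. The documents do not support that: they leave the route open without choosing it. What stands against the objection is that the three purposes are broad, and that the log itself says unplanned interim analyses may be done.

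**The discretion in Section 7.4 is qualified.** A reader might infer that the standards requirements named there must include the mean and SD limits. They could, because Section 9.6 defines a pass as satisfying the standard. They could equally mean counts and quotas, because Section 6.3.1 attributes the stratification to the same standard. The text does not settle it.

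**There is a count-based end.** Section 5.2 gives one, so it would be wrong to say that the plan has no end point. The accurate statement is that Sections 5.2 and 6.3.1 disagree. It would also be wrong to read 200 as a limit per stratum. It covers both arms together, and accuracy is judged by arm and analysis population.

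**The size depends on the case chosen.** This is fair. A look after every patient is the extreme, a true SD of 8.5 lies just over the limit, and 58 is an assumed ceiling. Section 9.2.1 sets errors inside the reference range to zero, so normal errors are only an approximation.

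**Most of the false-pass chance comes from elsewhere.** Also fair. About 28% is present at a fixed 27 with no looks at all, from a point-estimate rule at small numbers. The plan promises no error rate either. Optional stopping adds to that chance and reverses the benefit of enrolling more patients.

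**Conclusion.** The point holds as a permission that should be closed, not as a finding that enrolment will be stopped on accuracy. The sponsor may see unblinded data before closure, may continue or stop any group, and may enrol past the quotas under one of two conflicting statements. Nothing bars the running errors from informing those choices once the minimum quotas and pair targets are met.

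For a device just outside the SD limit, the added chance of passing in the illustration is about 9 percentage points with a look every 10 patients (28% to 37%) and 12 to 14 points with a look after every patient (28% to 40–42%). The gain is about 4 points at a true SD of 9 (9% to 13%) and negligible at 10. These figures rest on assumed SD, correlation, zero bias, normal errors, one pressure and an even share of the spare patients. Requiring both pressures to pass lowers the levels. The concern is one of credibility near the limit, where the accuracy decision is hardest.

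**What to change.** 1. Reconcile Sections 5.2 and 6.3.1 on when enrolment ends, and in the same edit reconcile the total of 83 with the arm minimums of 45 and 29.
2. State in Sections 5.2, 7.4 and 9.4 that continuing or stopping depends only on counts of evaluable patients and pairs and on the age, weight, sex, cuff and blood-pressure-range quotas.
3. State that NIBP minus IBP errors are not summarised for an arm and analysis population until its enrolment is declared closed.
4. State that any earlier access for safety, engineering or regulatory reasons is logged, reported and does not change the enrolment target.
5. State that all evaluable patients enrolled up to closure enter the analysis.

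The cost is protocol wording and an access log, with no added patients or procedures. The sponsor gives up using accuracy results to decide when to stop. The change does not remove the false-pass chance that a point-estimate rule carries at small numbers.
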